8.2.1.1. Inclusion Criteria

The following are the inclusion criteria for the study cohort:

- ≥1 prescription for DOACs of interest (index date)

8.2.1.2. Exclusion Criteria

The following are the exclusion criteria for the study cohort:

- Exclusion criteria applied during selection of the data cut:
 - <1 diagnosis code for AFib on index date or in 12 months prior (applied during selection of the data cut)
 - <1 risk factor for stroke other than Afib on index date or in 12 months prior defined by CHA₂DS₂ VASc >1 for men and >2 for women²⁶
 - <1 medical encounter in the 180 days prior to index date
 - ≥1 diagnosis code for the following conditions on index date or any time prior:
 - Cardiac valve disease (mitral stenosis, valvular replacement)
 - Deep vein thrombosis
 - Pulmonary embolism
- Exclusion criteria applied after selection of the data cut:
 - <18 years of age on index date
 - <12 months' registration with a GP prior to the index date
 - ≥1 prescription record for DOACs in the 12 months prior to the index date (i.e., prevalent users)
 - ≥1 diagnosis code for the study outcomes of interest (stroke, MI, TIA, major bleeding events) on index date or any time prior
 - ≥1 diagnosis code for the following conditions on index date or any time prior:
 - Angina
 - Congenital heart disease
 - Missing age
 - Missing gender

Comparative Effectiveness and Safety of DOACs in Patients with AFib in the UK

8.2.2. Study Periods

The study observation period spans July 1, 2013 through December 31, 2020, consisting of a drug indexing, baseline and follow-up periods (Figure 8.1). The drug indexing period will be used to ascertain DOACs initiation (index date). Baseline period is defined as 12 months prior to and including the index date. The follow-up period will include all available time after study index date. Patients will be followed in an “intention to treat” (ITT) approach from their index date until the end of follow-up period or the occurrence of the following events, whichever occurs first:

- First occurrence of the study outcomes of interest
- Death
- End of patient data
- End of patient registration with GP.

In addition, patients meeting the selection criteria will be followed in an “as-treated” approach from their index date until the end of the study follow-up period or the occurrence of the following events, whichever occurs first:

- First occurrence of the study outcomes of interest.
- Death
- End of patient data.
- End of patient registration with GP.
- Termination of exposure, crossover of exposure group, or addition of another DOAC.

Termination of exposure in the as-treated analysis is defined as having a gap exceeding 30 days (grace period) between the end of a prescription, based on its start date and duration, and the start of the next prescription, or if no additional prescription occurs. The termination date is defined as the prescription end date plus a 30-day risk window.

Comparative Effectiveness and Safety of DOACs in Patients with AFib in the UK

[figure not shown]

Figure 8.1 Study Design Diagram

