8.3.1. Exposures

DOACs of interest will include apixaban, rivaroxaban, edoxaban, and dabigatran. Exposures will be defined by corresponding ATC codes: B01AF02; B01AF01; B01AF03; and B01AE07, respectively. Initiators of DOACs are defined as new users of DOACs with no record of prescription for any DOAC during 12 months before index date.

Only a single index date is allowed per patient; if a patient qualifies as a new user of an exposure group multiple times, the patient will enter the cohort on the first qualifying exposure date. Patients with exposure to more than one DOAC on the index date will be excluded. Duration of treatment is calculated from the provided days supplied/duration data field. Fields with 0 are assumed to be 1 day. A grace period of 30 days between refills and risk window of 30 days after the last refill is used to define persistence. The operationalized definition of exposure will be recorded in the STaRT RWE template and is available on request.

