8.3.1.2. Secondary Exposure Groups

The following independent Exposure Groups will be created:

- *Exposure Group 3*: Initiators of edoxaban
- *Exposure Group 4*: Initiators of dabigatran
- *Exposure Group 5*: Initiators of rivaroxaban, edoxaban, and dabigatran
- *Exposure Group 6*: Initiators of apixaban, edoxaban, and dabigatran
- *Exposure Group 7*: Initiators of apixaban, rivaroxaban, and dabigatran
- *Exposure Group 8*: Initiators of apixaban, rivaroxaban, and edoxaban

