8.3.1.4. Secondary Comparisons

- *Secondary Comparison 1*: initiators of apixaban vs initiators of edoxaban (i.e., *Exposure Group 1 vs Exposure Group 3*)
- *Secondary Comparison 2*: initiators of apixaban vs initiators of dabigatran (i.e., *Exposure Group 1 vs Exposure Group 4*)
- *Secondary Comparison 3*: initiators of apixaban vs initiators of other DOACs class (i.e., *Exposure Group 1 vs Exposure Group 5*)
- *Secondary Comparison 4*: initiators of rivaroxaban vs initiators of edoxaban (i.e., *Exposure Group 2 vs Exposure Group 3*)
- *Secondary Comparison 5*: initiators of rivaroxaban vs initiators of dabigatran (i.e., *Exposure Group 2 vs Exposure Group 4*)
- *Secondary Comparison 6*: initiators of rivaroxaban vs initiators of other DOACs class (i.e., *Exposure Group 2 vs Exposure Group 6*)
-
- *Secondary Comparison 7*: Initiators of edoxaban vs initiators of other DOACs class (i.e., *Exposure Group 3 vs Exposure Group 7*)
- *Secondary Comparison 8*: initiators of dabigatran vs initiators of other DOACs class (i.e., *Exposure Group 4 vs Exposure Group 8*)

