This study will be based on secondary use data from EHR with inherent limitations, including misclassification. For example, a patient may not necessarily use a medication that they have received a prescription for; however, this is less likely in the case of medications for chronic conditions like cardiovascular diseases. Additionally, while it is possible to identify study

Comparative Effectiveness and Safety of DOACs in Patients with AFib in the UK

outcomes of interest in the THIN® database, misclassification of the outcome is possible, as the presence of a diagnosis in medical records does not necessarily indicate a true presence of disease; however, the outcomes of interest are included in the Quality and Outcome Framework (QOF)³⁴ which rewards and incentivizes GPs in England for quality care and coding of diagnoses. In addition, validated algorithms from previously published real-world studies will be used to define study variables of interest.

An incident user design will be applied to reduce biases that can impact non-randomized studies, especially when using EHR.³⁵ An ITT analysis will be used because it has the advantage of eliminating certain types of biases by preserving the prognostic balance obtained through the propensity score matching and maintaining sample size;^{36,37} however, ITT analysis is sometimes considered to be “too conservative” and has the possibility of exposure misclassification.^{35,36} Additionally, “as-treated” approach will be used that will censor individuals upon discontinuation of index treatment or treatment crossover. However, limitations of an “as-treated” analysis include the possibility of introducing certain biases including differential and informative censoring, or time-dependent confounding biases.^{36,37}

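### The as-treated censoring rule names no switch to a vitamin K antagonist, and leaves open whether a switch within a pooled DOAC arm ends follow-up

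*Protocol*

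**What the plan says.** Section 8.2.2 lists the events that end as-treated follow-up. The one that separates it from the ITT list is "Termination of exposure, crossover of exposure group, or addition of another DOAC". Termination is then defined as "having a gap exceeding 30 days (grace period) between the end of a prescription" and "the start of the next prescription, or if no additional prescription occurs", and is dated at the prescription end plus a 30-day risk window. The definition does not name the drug of the next prescription.

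Section 8.3.1 restates the rule in terms of refills: "A grace period of 30 days between refills and risk window of 30 days after the last refill is used to define persistence". It places the operational exposure definition in the STaRT-RWE template.

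Section 8.3.1.2 builds Exposure Groups 5 to 8 by pooling three DOACs each. Group 5, for example, is "Initiators of rivaroxaban, edoxaban, and dabigatran". Section 8.3.1.4 sets each pool against the remaining single drug, as in Secondary Comparison 3: "initiators of apixaban vs initiators of other DOACs class". Comparisons 6, 7 and 8 have the same form.

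Section 10 says that the as-treated approach will "censor individuals upon discontinuation of index treatment or treatment crossover".

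**The concern.** An as-treated analysis is meant to attribute person-time to the drug being taken. The rule falls short of that in two ways.

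A move from a DOAC to warfarin ends exposure to the index drug as surely as a move to another DOAC does, yet only the second is a trigger. Events on the VKA, bleeding included, that occur before the prescription end plus 30 days are counted against the DOAC. This reaches the primary comparison.

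In the drug-versus-class comparisons, the rule can be programmed so that one arm measures time on the first drug and the other measures time on any of three drugs. If switching follows bleeding, intolerance or another change in prognosis, post-switch time would then be kept in one arm only, and censoring would be differential by construction.

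**Working it through.** The protocol gives no figure to reproduce on this point. The check is textual, with an illustration of size.

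**Switch to a VKA.** Take each trigger in turn for an apixaban initiator given warfarin part-way through a prescription.
- Crossover of exposure group: none of Groups 1 to 8 contains a VKA, so this is not met.
- Addition of another DOAC: warfarin is not a DOAC, so this is not met.
- Termination: met only through the gap rule, and dated at prescription end plus 30 days.

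Days attributed to the DOAC after the switch = (L − t) + 30, where L is the prescription length and t the day of the switch. The protocol gives no typical L. Assuming L = 56:
- t = 1: 55 + 30 = 85 days
- t = 28: 28 + 30 = 58 days
- t = 56: 0 + 30 = 30 days

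A switch to another DOAC on the same day t would end follow-up at the switch.

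**Switch within a pooled arm.** Take a rivaroxaban initiator who finishes a prescription and starts edoxaban within 30 days. This patient belongs to Groups 2, 5, 7 and 8.
- Group 2 (rivaroxaban alone): edoxaban is outside the group, so the patient has crossed and is censored.
- Group 5 (rivaroxaban, edoxaban, dabigatran): no crossover. There is no gap over 30 days if any DOAC counts as the next prescription, and no addition if a replacement is not one. Follow-up continues.
- Group 7 (apixaban, rivaroxaban, dabigatran): crossed and censored.
- Group 8 (apixaban, rivaroxaban, edoxaban): as Group 5, follow-up continues.

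On this reading one patient has different as-treated end dates in different comparisons. If instead the refill wording of Section 8.3.1, the index-treatment wording of Section 10 or the addition trigger is applied by drug, the patient is censored in all four groups.

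**Illustrative size of the second defect.** Inputs:
- Horizon T = 2.3 years, the median follow-up in Table 9.1. It is not as-treated time and serves only as a horizon.
- Assumed: switching s = 2%, 5% or 10% per year; discontinuation d = 20% per year; share w of class-arm switches that stay in the class = 1/3, 2/3 or 0.9.
- Constant hazards. Death, outcome events and administrative censoring are ignored.

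Hazard of as-treated censoring: single-drug arm h = d + s; class arm h = d + s(1 − w).
Proportion censored by a switch: single s/h × (1 − exp(−hT)); class s(1 − w)/h × (1 − exp(−hT)).
Mean person-time: (1 − exp(−hT))/h.

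Example, s = 0.05 and w = 2/3:
- Single: h = 0.25; 0.05/0.25 × (1 − exp(−0.575)) = 8.7%; person-time 1.749 years.
- Class: h = 0.2167; 0.0167/0.2167 × (1 − exp(−0.498)) = 3.0%; person-time 1.811 years.
- Ratio 1.811/1.749 = 1.036.

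| s per year | Single-drug arm censored by switch | Class arm, w = 1/3, 2/3, 0.9 | Person-time ratio class/single, w = 1/3, 2/3, 0.9 |
|---|---|---|---|
| 2% | 3.6% | 2.4%, 1.2%, 0.4% | 1.007, 1.014, 1.019 |
| 5% | 8.7% | 5.9%, 3.0%, 0.9% | 1.018, 1.036, 1.048 |
| 10% | 16.6% | 11.5%, 5.9%, 1.8% | 1.035, 1.071, 1.098 |

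With one drug-level rule in both arms (w = 0), the proportions are equal and the ratio is 1.000.

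**The case against.** A reader might infer that the plan definitely censors the two arms of a class comparison unequally. The document does not support that. The addition trigger is defined by drug, a refill ordinarily means more of the same drug, and Section 10 speaks of the index treatment. Together these make a drug-level rule a fair reading. It can be argued that counting every new DOAC as an addition would leave the crossover trigger with nothing to do, but overlapping triggers in a first-to-occur list are common and harmless. What remains is that no sentence says whether a within-class replacement ends follow-up, and that index treatment is not defined for a pooled group.

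The STaRT-RWE template may settle the matter and is not at hand. That does not dispose of the point: the protocol states the rule itself, in three differing forms, and Section 11 commits to following the protocol strictly.

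Following patients for as long as they stay in their pool is also a coherent estimand for a class comparison. It would have to be chosen openly, since the single-drug arm is then held to a different standard, and it does not match Section 10.

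A reader might also put the affected share of the class arm at 7-14%: (1 − exp(−0.05 × 2.3)) × 2/3 = 0.072 and (1 − exp(−0.10 × 2.3)) × 2/3 = 0.137. This ignores discontinuation. With the assumed 20% per year it becomes 8.7% × 2/3 = 5.8% and 16.6% × 2/3 = 11.1%. It also assumes equally likely switch targets, although Section 6.1 says that apixaban and rivaroxaban are the most prescribed. In Comparison 3 the likeliest target, apixaban, lies outside the pool. In Groups 7 and 8 the within-class share could be higher.

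On the VKA point, the fair reply is that 85 days is a worst case, that 30 of those days are a declared risk window given to everyone who stops, and that both arms are treated alike. All of that stands. It limits the size, but it does not explain why a DOAC switch is a trigger and a VKA switch is not. Section 10 already concedes informative censoring in as-treated analyses. That is a general caveat and does not define the censoring event.

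**Conclusion.** The VKA omission holds without ambiguity and applies to every as-treated comparison, the primary one included. For a switch during an assumed 56-day prescription, 30 to 85 days after the switch are attributed to the DOAC. How many patients this affects cannot be said, because the protocol gives no rate of switching to a VKA.

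The pooled-arm point holds as an ambiguity. The sections permit unequal censoring in the as-treated versions of Secondary Comparisons 3, 6, 7 and 8, and other wording points the other way. Under the assumed rates, the class/single person-time ratio would be about 1.01-1.10 if the group-level reading were programmed. The person-time shift is modest; the greater concern is that post-switch time would be selected in one arm only.

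No bias in any hazard ratio is shown, in size or direction. For the VKA defect, differential bias would need VKA switching, or its consequences, to differ between the drugs. The ITT analyses are unaffected by either defect, and the second does not touch the primary comparison or the drug-versus-drug secondary comparisons.

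**What to change.** In Section 8.2.2, replace the last as-treated bullet with one rule: follow-up ends at termination of the index drug or at the first prescription of any other oral anticoagulant (DOAC or VKA), whichever comes first. State that the 30-day gap rule counts prescriptions of the index drug only, and that the rule applies alike to both arms of every comparison, including pooled Groups 5 to 8, where the index drug is the one the patient initiated. Align the persistence sentence in Section 8.3.1 and the as-treated sentence in Section 10.

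The cost is one sentence, two alignments and one censoring variable. The data are prescription records that the study already uses; the planned subgroup of prior warfarin users in Section 9 relies on warfarin records too. The downside is slightly less as-treated person-time.

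### Read literally, the as-treated stop rule times each gap from one prescription's own end date, so some patients with supply in hand would be permanently censored

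*Protocol*

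**What the plan says.** Section 8.2.2 defines termination of exposure for the as-treated follow-up as "a gap exceeding 30 days (grace period) between the end of a prescription, based on its start date and duration". The gap is counted to whichever prescription follows, and having no further prescription also counts as termination. The section then fixes the censoring date: "The termination date is defined as the prescription end date plus a 30-day risk window". Follow-up ends at the first of several listed events, one of which is "Termination of exposure, crossover of exposure group, or addition of another DOAC".

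Section 8.3.1 supplies the ingredients. "Duration of treatment is calculated from the provided days supplied/duration data field", and a zero in that field is set to one day. "A grace period of 30 days between refills and risk window of 30 days after the last refill is used to define persistence". Also, "Only a single index date is allowed per patient", and neither section describes re-entry after a stop.

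Neither section mentions prescriptions issued early, issued together, or nested one inside another. Section 8.3.1 adds: "The operationalized definition of exposure will be recorded in the STaRT RWE template and is available on request". That template is not part of the protocol.

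**The concern.** The end of a prescription is tied to that prescription's own start and duration. If records are taken in date order, days still in hand from an earlier prescription count for nothing once a later one has been issued. A patient who never ran out can then show a gap of more than 30 days and be treated as having stopped.

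Each such stop removes all of that patient's later on-treatment time and events from the as-treated hazard ratio, for a reason that lies in how prescriptions were issued and not in drug use. Section 10 already names differential and informative censoring as a weakness of the as-treated approach; this would be an avoidable addition to it. The same grace period and risk window define persistence, which is a criterion in the Table 9.1 checklist, so persistence would be understated as well.

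**Working it through.** The protocol states no figure that depends on this rule, so there is none to reproduce. The check applies the rule as written to hypothetical prescription sequences.

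**Rule from 8.2.2.** End = start + own duration. Stop if (next start − end) > 30. Censor at end + 30.

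**Alternatives.** (i) Measure the gap from the latest end date of any prescription already issued. (ii) Carry unused days forward onto the next prescription.

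| Sequence (days) | Own end | Gap as written | Result as written | (i) Latest end date | (ii) Carry-over |
|---|---|---|---|---|---|
| Two 56-day on 0; next 112 | 56 | 56 | stop, 86 | gap 56, stop | supply to 112, no stop |
| Six 28-day, each 7 days early (0 to 105); next 168 | 133 | 35 | stop, 163 | gap 35, stop | supply to 168, no stop |
| Five 28-day, each 7 days early (0 to 84); next 140 | 112 | 28 | no stop | no stop | no stop |
| Two 28-day on 0; next 56 | 28 | 28 | no stop | no stop | no stop |
| 84-day on 0, 7-day on 60; next 105 | 67 | 38 | stop, 97 | end 84, gap 21, no stop | supply to 91, gap 14, no stop |
| 84-day on 0, zero-duration record on 40 (1 day); next 84 | 41 | 43 | stop, 71 | end 84, gap 0, no stop | no stop |
| 56-day on 0, 28-day on 10; next 84 | 38 | 46 | stop, 68 | end 56, gap 28, no stop | supply to 84, no stop |

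**What decides it.** Measured gap = true supply gap + days still in hand at the last record's own end date. With no true gap, a stop needs more than 30 days in hand that are then used before the next prescription. One same-day double issue of length D, run down fully, gives a gap of D: no stop at 14, 28 or 30 days, a stop at 31, 56 or 84. A patient who always refills early and never draws the surplus down is not stopped. In the nested cases no stockpile is needed, because the days in hand can simply be the rest of an ordinary longer prescription.

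**Size under assumptions.** None of the prescription lengths, refill spreads or double-issue rates below is in the protocol. The horizon is the 2.3-year median follow-up in Table 9.1 (2.3 × 365.25 = 840 days).

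- *Early refills only.* Simulated refill intervals had a mean equal to the prescription length (28, 56 or 84 days), and only patients with no supply gap were kept. Falsely stopped: 0% at an SD of 3 or 7 days, 0.3% to 1.9% at SD 10, 3.7% to 22% at SD 14. A different refill model (reserve at refill centred on 7 days, truncated at 0) gave 0% at SD 5 and 3.7% to 11.6% at SD 10.
- *Double issues, 56-day prescriptions.* Let p be the chance per issue that two are issued together and then fully run down. By 840 days there are 840/56 = 15 issues, and the share with such an event is 1 − (1 − p)^15 = 7.2%, 14.0% and 26.1% for p = 0.5%, 1% and 2%. The stop itself falls 86 days after the double issue, so the exponent should be (840 − 86)/56 = 13.46. That gives 6.5%, 12.7% and 23.8% stopped, with about 3.0%, 5.8% and 11.2% of on-treatment time lost.
- *Double issues, 28-day prescriptions.* A single double issue gives 0%.

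**The case against.** The strongest reply is that the protocol is silent on overlap and does not say that it is ignored. The operational definition is left to the STaRT-RWE template, which could contain carry-over, and section 11 lets variable definitions be modified. This stands in part: nobody can say from the protocol that the programmed algorithm has the fault. But 8.2.2 does state how the end date is derived, section 11 says the protocol will be strictly followed with changes documented in amendments, and a template with carry-over would depart from the sentence in 8.2.2. The text needs an edit either way.

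The nested examples also depend on taking the shorter record as the prescription from which the gap runs. Measured from the 84-day prescription, the gap to day 105 is 21 days and there is no stop. That is a sensible reading, but the wording does not secure it.

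Three stronger inferences are tempting and are not supported:

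- That continuously supplied patients in general are stopped. The grace period absorbs any surplus of 30 days or less.
- That a quarter of users would be lost. The upper percentages need 56-day prescriptions, an assumed double-issue rate, full run-down each time, and continuous use for 2.3 years, which Table 9.1 gives as median follow-up and not as time on drug.
- That the hazard ratio is biased between arms, or that the persistence check fails. Nothing shows that issuing patterns differ by drug, and the persistence criterion has no fixed threshold.

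Finally, the data are written prescriptions. An early issue may replace lost tablets or follow a change of strength, so carry-over has its own misclassification. That stands, and it is why carry-over needs a cap and should not be the only analysis.

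**Conclusion.** The point holds in limited form. Followed as written, 8.2.2 misdates the stop for some patients who still have supply, and the censoring is permanent. Two groups are exposed: patients who accumulate and then use more than 30 days of surplus, and patients with a short or zero-duration record nested in a longer prescription. Only the as-treated analysis and the persistence description that shares its rule are affected; the ITT follow-up does not use it. The share affected cannot be computed from the protocol and runs from none to a material share, depending on assumed prescription length and refill pattern. Censoring that differs by arm is possible but not shown. The conclusion rests on a literal reading of 8.2.2 and on the unseen template not overriding it. It is worth correcting before the as-treated analysis is run, but it does not threaten the study as a whole.

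**What to change.** In 8.2.2 and 8.3.1:

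1. Measure the 30-day gap, and date the termination, from the latest end date of any same-drug prescription already issued. This removes the nested cases, including zero-duration records, and adds no days beyond what some issued prescription already covers.
2. Also run the as-treated analysis with unused same-drug supply carried forward up to a stated cap, chosen before outcomes are viewed. This is needed for double issues and accumulated early refills, which step 1 does not reach.
3. Report the rule as now written as a sensitivity analysis, and make the STaRT-RWE template agree with the amended text.

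A tabulation in the diagnostic phase of prescription lengths, overlaps and zero-duration records would show how much this matters without touching outcomes.

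The cost is a change to the exposure algorithm, a re-run and a short amendment, with no new data. The downside is that carry-over can overstate exposure when an early issue is a replacement or a strength change; the cap and the retained present rule show how far that matters.
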